## 10.5 Appendix: Contingency measures for a regional or national emergency that is declared by a governmental agency

Continuation of the study in the event of a regional or national emergency declared by a governmental agency:

A regional or national emergency declared by a governmental agency (eg, public health emergency, natural disaster, pandemic, terrorist attack) may prevent access to the clinical trial site.

Contingency procedures are suggested below and in [Sections 5.5, 6.4, 7.1.1, 8, 9.4.4, and 10.1.3](#) for an emergency that prevents access to the study site, to ensure the safety of the participants, to consider continuity of the clinical study conduct, protect study integrity, and assist in maintaining compliance with Good Clinical Practice in Conduct of Clinical Trials Guidance. Sponsor agreement MUST be obtained prior to the implementation of these procedures for the duration of the emergency.

During the emergency, if the site will be unable to adequately follow protocol mandated procedures, alternative treatment outside the clinical study should be proposed, and enrollment, randomization, administration of study intervention, and blood sampling may be temporarily delayed/halted (see also [Section 5.5](#)).

Attempts should be made to perform all assessments in accordance with the approved protocol to the extent possible. In case this is not possible due to a temporary disruption caused by an emergency, focus should be given to assessments necessary to ensure the safety of participants and those important to preserving the main scientific value of the study.

Procedures to be considered in the event of a regional or national emergency declared by a governmental agency:

- If onsite visits are not possible, remote visits (eg, with home nurses, home health vendor, etc.) may be planned for the blood collection and collection of possible safety data,
- If onsite visits are not possible visit windows may be extended for assessment of safety and/or data that cannot be obtained remotely.

Contingencies implemented due to emergency will be documented.

## 10.6 Appendix: Risk-based Approach

ICH E6-R2 guideline for GCP is introducing the « risk-based approach » concept which permits to focus efforts on what is critical for a study and most specifically on Critical Data and Critical Processes. Critical data and processes are defined for the study with associated risks in the Study Risk Management Plan.

## 10.7 Appendix: Abbreviations

1/dil	1/dilution
Ab	antibody
AE	adverse event
AESI	adverse event of special interest
AR	adverse reaction
BARDA	Biomedical Advanced Research and Development Authority
CBER	Center for Biologics Evaluation and Research
CDISC	Clinical Data Interchange Standards Consortium
CFR	Code of Federal Regulation
CI	confidence interval
CIOMS	Council for International Organizations of Medical Sciences
CNIL	Commission Nationale de l'Informatique et des Libertés
COVID-19	Coronavirus Disease 2019
CRB	case report book
CRF	case report form
CSR	clinical study report
D	day
DNA	deoxyribonucleic acid
ECG	Electrocardiogram
eDiary	electronic diary
ELISA	enzyme-linked immunosorbent assay
FAS	full analysis set
FDA	Food and Drug Administration
FSH	Follicle stimulating hormone
GCP	Good Clinical Practice
GDPR	General Data Protection Regulation
GLA/SE	Glucopyranosyl Lipid A in stable oil-in-water emulsion
GMT	geometric mean titer
GPV	Global Pharmacovigilance
HA	hemagglutinin
HAI	hemagglutination inhibition
HCG	human chorionic gonadotropin
HIH	hemagglutination inhibition using horse red blood cells
HIPAA	Health Insurance Portability and Accountability Act

---

HRBC	horse red blood cells
HRT	Hormonal replacement therapy
IB	Investigator's Brochure
ICF	informed consent form
ICH	International Council for Harmonisation
IEC	Independent Ethics Committees
IM	intramuscular
IMP	Investigational Medicinal Product
IRB	Institutional Review Boards
IRT	interactive response technology
LLT	lowest level term
MAAE	medically attended adverse event
MDCK	Madin-Darby canine kidney
MedDRA	Medical Dictionary for Regulatory Activities
NA	neuraminidase
NIMP	Non- Investigational Medicinal Product
NT	Neutralization
PPAS	Per-protocol analysis set
PSC	Protein Sciences Corporation
PT	preferred term
PV	pharmacovigilance
QTL	quality tolerance limits
RCDC	reverse cumulative distribution curve
rHA	recombinant hemagglutinin
RMO	Responsible Medical Officer
RNA	ribonucleic acid
SAE	Serious adverse events
SafAS	Safety Analysis Set
SAP	Statistical analysis plan
SARS-COV-2	severe acute respiratory syndrome coronavirus 2
SE	stable emulsion
SIP	Shared Investigator Platform
SN	seroneutralization
SoA	Schedule of Activities
SOC	system organ class

SUSAR      suspected unexpected serious adverse reactions  
TBD          to be determined  
V              visit  
WOCBP        Woman of Childbearing Potential

### Version History

Not applicable as this is the first version of the SAP Core Body.

Previous Version(s)*	Date	Comments (optional)
NA	27MAY2022	

## 1 Overall Design

The design of the study is summarized in [Table 1.1](#)

**Table 1.1: Overall design**

Type of design	Randomized study, enrolling naive participants, 2-dose, modified double-blind. As the study will include adjuvanted study vaccines that may have a different appearance than the unadjuvanted vaccine, personnel assessing the immunogenicity and safety of the investigational vaccines with the goal of dose selection for the pivotal Phase III study in adults
Phase	I/II
Control method	Active comparator (comparator = Panblok H7 (45 µg) unadjuvanted)
Study population	Healthy adults 18 - 64 and $\geq$ 65 years of age
Level and method of blinding	Modified double-blind (participant, Sponsor, and Investigator blinded)
Study intervention assignment method	Randomization and stratification by age group Randomization ratio is: 3:3:1 (Study Group 1, Group 2, and Group 3)
Number of participants	Approximately 700 adult participants (350 adults 18 - 64 years of age and 350 adults $\geq$ 65 years of age)
Intervention groups	Two of the three Investigational Medicinal Products (IMPs) include the MF59 adjuvant.  The IMPs included in this study are: Panblok H7 (7.5 µg) + MF59 (Group 1): Monovalent Recombinant H7 influenza vaccine [A/Guangdong/17SF003/2016 (H7N9)] with MF59  Panblok H7 (15 µg) + MF59 (Group 2):

	
Monovalent Recombinant H7 influenza vaccine [A/Guangdong/17SF003/2016 (H7N9)] with MF59
 
Panblok H7 (45 µg) unadjuvanted (Group 3): Monovalent Recombinant H7 influenza vaccine [A/Guangdong/17SF003/2016 (H7N9)]

Total duration of study participation	A pre-vaccination (baseline) blood sample will be taken during Visit (V) 01 (D01) and post-vaccination blood samples will be taken during V02, V03, V04, and V05 (i.e., D22, D43, D202, and D387) for HIH and SN testing to assess the immune response after Dose 1 and Dose 2 of the study intervention and to assess the persistence of the immune response at 6 and 12 months after the last vaccination
Countries	United States of America
Use of an Independent Data Monitoring Committee, Dose-Escalation Committee, or similar review group	Periodic safety management team (SMT) meetings

***Number of Participants:***

A total of 700 participants is expected to be randomized with the aim to obtain a total of 630 evaluable participants.

	Group 1: Panblok H7 (7.5 µg) + MF59		Group 2: Panblok H7 (15 µg) + MF59		Group 3: Panblok H7 (45 µg) unadjuvanted		Total
	18 - 64 years	≥ 65 years	18 - 64 years	≥ 65 years	18 - 64 years	≥ 65 years	
Planned number of Participants	150	150	150	150	50	50	700

***Estimation of the Number of Sites:*** Approximately 14 active sites

The graphical design of Study VAM00001 is presented in [Figure 1.1](#).

**Table 1.2: Schedule of activities**

**Phase I/II Study, 5 Visits, 2 Vaccinations, 5 Blood Samples, 13 Months' Duration Per Participant**

Visit/Contact	Collection of information in the CRF	Visit 1	Visit 2	Visit 3	Visit 4	Visit 5
Study timelines (days)		D01	21 days post V01 (D22)	21 days post V02 (D43)	6 months post V02 (D202)	12 months post V02 (D387)
Time windows (days)			[+7 D]	[+7 D]	[+14 D]	[+14 D]
Visit procedures:						
Informed consent	X	X				
Inclusion/exclusion criteria	X	X				
Collection of demographic data	X	X				
Urine pregnancy test (if applicable)		X	X			
Collection of Medical history	X Significant Medical History	X				
Physical examination		X	X			
Temporary and definitive contraindications	X		X			
Pre-vaccination temperature		X	X			
Randomization	X	X				
Allocation of participant number	X	X				
Dose assignment by IRT		X	X			
Blood sampling (BL) [40 mL/visit]	X	BL0001 Pre-vac	BL0002 Pre-vac	BL0003	BL0004	BL0005
Vaccination (vac)	X	X	X			

Visit/Contact	Collection of information in the CRF	Visit 1	Visit 2	Visit 3	Visit 4	Visit 5
Visit/Contact	Collection of information in the CRF	Visit 1	Visit 2	Visit 3	Visit 4	Visit 5
Diary card/eDiary provided†		DC1/eDC	DC2	DC3	DC4	
Diary card/eDiary reviewed			DC1/eDC	DC2/eDC	DC3/eDC	DC4/eDC
Diary card collected‡			DC1	DC2	DC3	DC4
Collection of solicited injection site and systemic reactions	X	X	X	X		
Collection of unsolicited adverse events (AEs)	X	X	X	X		
Collection of concomitant medications	X Reportable concomitant medication	X	X	X		
Collection of serious adverse events (SAEs), including AESIs	X	To be reported at any time during the study				
Collection of pregnancies	X	To be reported at any time during the study				
End of Study Intervention Phase§	X			X		
End of study**	X					X

AESI: adverse event of special interest; CRF: case report form; D: day; DC: diary card; IRT: interactive response technology; V: visit

[figure not shown]
† The investigator or an authorized designee will remind the participants to bring back the DC at the next visit and will answer any questions.

‡ The investigator or an authorized designee will interview the participants to collect the information recorded in the DC and will attempt to clarify anything that is incomplete or unclear.

§ In case of participant discontinuation at a visit, the entire visit will be completed.

\*\* All participants will be scheduled to attend V05 for blood sampling and safety follow-up. However, if any participants discontinue the study early, they are still to be followed for safety and are to be contacted by phone to identify the occurrence of any SAEs and AESIs that had not yet been reported. The site should attempt to contact them and complete the 12-month safety follow-up (and all other scheduled safety follow-ups), except if they specified that they do not want to be contacted again and it is documented in the source document.

**Figure 1.1: Graphical study design**

BL: Blood sample

VAC: vaccination

Detailed design is provided in Section 4.1 of the protocol.

## 2 Objectives and Endpoints

**Table 2.1: Objectives and endpoints**

Objectives	Endpoints

Primary
 
To assess the antibody response induced by each study dose group of Panblok H7+MF59 vaccine (7.5 µg and 15 µg) compared with unadjuvanted Panblok H7 (45 µg) by hemagglutination inhibition using horse red blood cells (HIH) and seroneutralization (SN) measurement methods at day (D) 22 and D43 (i.e., 21 days after each vaccination) in participants 18 - 64 years and <math>\geq</math> 65 years of age
	
Immunogenicity
 
The following immunogenicity endpoints will be summarized:
 
Immunogenicity by HIH measurement method:
 
 
• Hemagglutination inhibition (HAI) antibody (Ab) titers obtained on D01, D22, D43, D202, and D387
 
• Individual HAI Ab titers ratio D22/D01, D43/D01, D202/D01, D387/D01, D22/D202, D22/D387, D202/D43 and D387/D43
 
• Seroconversion defined as titer <math><</math> 10 (1/dilution [1/dil]) on D01 and post-injection titer <math>\geq</math> 40 (1/dil) on D43 or defined as titer <math>\geq</math> 10 (1/dil) on D01 and a <math>\geq</math> 4-fold increase in titer (1/dil) on D43.
 
 
Seroconversion defined as titer <math><</math> 10 (1/dilution [1/dil]) on D01 and post-injection titer <math>\geq</math> 40 (1/dil) on D22 or defined as titer <math>\geq</math> 10 (1/dil) on D01 and a <math>\geq</math> 4-fold increase in titer (1/dil) on D22.
 
 
• Individual HAI Ab titers <math>\geq</math> 40 (1/dil) on D01, D22, D43, D202, and D387
 
• Detectable HAI Ab titer, i.e., with a titer <math>\geq</math> 10 (1/dil) on D01, D22, D43, D202, and D387
 
 
Immunogenicity by SN measurement method:
 
 
• Neutralization (NT) Ab titer obtained on D01, D22, D43, D202, and D387
 
• Individual NT Ab titers ratio D22/D01, D43/D01, D202/D01, D387/D01, D22/D202, D22/D387, D202/D43 and D387/D43
 
• NT Ab titers <math>\geq</math> 20 (1/dil), <math>\geq</math> 40 (1/dil), <math>\geq</math> 80 (1/dil) on D01, D22, D43, D202, and D387
 

Objectives	Endpoints
	

• Fold increase in NT Ab titer [D43/pre-vaccination] <math>\geq 2</math> and <math>\geq 4</math> on D43

• Fold increase in NT Ab titer [D22/pre-vaccination] <math>\geq 2</math> and <math>\geq 4</math> on D22

• Detectable NT Ab titer, i.e., with a titer <math>\geq 10</math> (1/dil) on D01, D22, D43, D202, and D387

Secondary	
Safety
 
To assess the safety profile in each study vaccine group in participants 18 - 64 years and <math>\geq 65</math> years of age throughout the study
 
Safety
 
The following safety endpoints will be summarized:
 

• Presence of any unsolicited systemic adverse events (AEs) reported in the 30 minutes after each vaccination

• Presence of solicited (prelisted in the participant's diary card [DC] / electronic diary card [eDC] and case report book [CRB]) injection site reactions and systemic reactions occurring up to 7 days after each / any vaccination

• Presence of unsolicited AEs up to 21 days after each / any vaccination

• Presence of adverse events of special interest (AESIs) throughout the study

• Presence of serious adverse events (SAEs) (including AESIs) throughout the study

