## 1.2 Schedule of Activities (SoA)

**Table 2.1 - Schedule of activities**

**Phase I/II Study, 5 Visits, 2 Vaccinations, 5 Blood Samples, 13 Months' Duration Per Participant**

Visit/Contact	Collection of information in the CRF	Visit 1	Visit 2	Visit 3	Visit 4	Visit 5
Study timelines (days)		D01	21 days post V01 (D22)	21 days post V02 (D43)	6 months post V02 (D202)	12 months post V02 (D387)
Time windows (days)			[+7 D]	[+7 D]	[+14 D]	[+14 D]
Visit procedures:						
Informed consent	X	X				
Inclusion/exclusion criteria	X	X				
Collection of demographic data	X	X				
Urine pregnancy test (if applicable)		X	X			
Collection of Medical history	X Significant Medical History*	X				
Physical examination		X	X			
Temporary and definitive contraindications	X		X			
Pre-vaccination temperature		X	X			
Randomization	X	X				
Allocation of participant number	X	X				
Dose assignment by IRT		X	X			
Blood sampling (BL) [40 mL/visit]	X	BL0001 Pre-vac	BL0002 Pre-vac	BL0003	BL0004	BL0005
Vaccination (vac)	X	X	X			

Visit/Contact	Collection of information in the CRF	Visit 1	Visit 2	Visit 3	Visit 4	Visit 5
eDiary provided†		X				
eDiary reviewed‡			X	X	X	X
Collection of solicited injection site and systemic reactions	X	X	X	X		
Collection of unsolicited adverse events (AEs)	X	X	X	X		
Collection of concomitant medications	X Reportable concomitant medication	X	X	X		
Collection of medically attended AEs (MAAEs)	X	To be reported at any time during the study				
Collection of serious adverse events (SAEs), including AESIs	X	To be reported at any time during the study				
Collection of pregnancies	X	To be reported at any time during the study				
End of Study Intervention Phase§	X			X		
End of study**	X					X

AESI: adverse event of special interest; CRF: case report form; D: day; DC: diary card; IRT: interactive response technology; V: visit

\* Significant medical history is described in [Section 8.2.1](#) of the protocol

† Electronic diary application should be downloaded to the participant's electronic device (such as mobile phone or tablet).

‡ Electronic diary is the primary method for safety data collection. However, paper diary cards will also be available for use as a back-up solution in case of major breakdown of the app or as determined by the Sponsor's study clinical team.

§ In case of participant discontinuation at a visit, the entire visit will be completed.

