\*\* All participants will be scheduled to attend V05 for blood sampling and safety follow-up. However, if any participants discontinue the study early, they are still to be followed for safety and are to be contacted by phone to identify the occurrence of any MAAEs, SAEs, and AESIs that had not yet been reported. The site should attempt to contact them and complete the 12-month safety follow-up (and all other scheduled safety follow-ups), except if they specified that they do not want to be contacted again and it is documented in the source document.

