
Safety
 
To assess the safety profile in each study vaccine group in participants 18 - 64 years and <math>\geq</math> 65 years of age throughout the study
	
Safety
 
The following safety endpoints will be described:
 

• Presence of any unsolicited systemic AEs reported in the 30 minutes after each vaccination

• Presence of solicited (prelisted in the participant's eDiary and CRB) injection site reactions and systemic reactions occurring up to 7 days after each / any vaccination

• Presence of unsolicited AEs up to 21 days after each / any vaccination

• Presence of MAAEs throughout the study

• Presence of AESIs throughout the study

• Presence of SAEs (including AESIs) throughout the study

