## 9 Statistical Considerations

All statistical analyses will be performed under the responsibility of the Sponsor's Biostatistics Platform using the SAS® software, Version 9.4 or above.

The SAP core body will be written and peer-reviewed before the initiation of the study. In accordance with the protocol, the SAP core body will describe all analyses to be performed by the Sponsor.

For descriptive purposes, the following statistics will be presented:

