### ***Medically Attended Adverse Events***

MAAE safety summaries will be reported for within 21 days after each vaccination, from D01 to D42, from D43 to D202, from D203 to D387, and overall study.

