#### 4.2.2.2.4 Time of Onset

Time of onset is derived from the start date of the unsolicited AE and the date of vaccination:

Time of Onset = start date of the unsolicited AE - date of vaccination + 1 (if D01 is the first vaccination day).

The time of onset is considered as missing only if one or both dates are missing or partially missing.

The unsolicited AEs will be analyzed “Within 21 days” after each vaccination, which corresponds to AEs with a time of onset between D01 and D22 or missing. An AE with missing time of onset will be considered to have occurred just after the vaccination, so will be included in these tables.

Time of onset period is displayed as D01-D04, D05-D08, D09-D15, D16 or later, and missing.

**Note:** Unsolicited AE that occurred before vaccination (negative time of onset) or with a time of onset higher than defined above will not be included in analysis but will be listed separately.

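### The SAP core body omits the protocol's secondary MAAE endpoint and has no rule to produce its planned summaries

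*SAP*

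**What the plan says.** **Protocol.** Table 3.1 lists "Presence of MAAEs throughout the study" as one of six secondary safety endpoints. Section 9.4.3 asks for MAAE summaries over the 21 days following each dose, then "from D01 to D42, from D43 to D202, from D203 to D387, and overall study". The schedule of activities (1.2) has an MAAE row, marked for CRF collection at any time in the study. Its end-of-study footnote has early discontinuers "contacted by phone to identify the occurrence of any MAAEs, SAEs, and AESIs that had not yet been reported". Section 9 states that "the SAP core body will describe all analyses to be performed by the Sponsor".

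**SAP core body.** Table 2.1 repeats five of the six safety endpoints. The entry after unsolicited AEs is "Presence of adverse events of special interest (AESIs) throughout the study", followed by SAEs. The schedule (Table 1.2) has no MAAE row, and its matching footnote reads "contacted by phone to identify the occurrence of any SAEs and AESIs that had not yet been reported". Sections 4.2.2.2.6 and 4.2.2.2.7 give SAEs and AESIs their own windows out to 387 days after each dose. For unsolicited AEs, 4.2.2.2.4 analyses onsets from D01 to D22 after a dose, or with missing onset; an unsolicited AE "with a time of onset higher than defined above will not be included in analysis but will be listed separately". Section 5, where departures from the planned analyses would be declared, has nothing to declare.

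**The concern.** The two current documents give different lists of secondary safety endpoints, and the one meant to describe every analysis has the shorter list. A programmer working from the core body would produce no MAAE rate by study group or age stratum. The same programmer would also have a rule that moves late non-serious MAAEs out of the tables and into listings, although the protocol asks for summaries of those periods. Collecting MAAEs throughout the study was a regulator's request, recorded in the protocol's rationale for version 2.0. It would be awkward to collect the data and then have no SAP rule for summarising them.

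**Working it through.** Neither document states a figure that can be reproduced here. The check is a comparison of the two texts, followed by a count of days.

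**1. Where MAAEs appear.**

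| Item | Protocol | SAP core body |
|---|---|---|
| Endpoint list | Table 3.1: yes | Table 2.1: no |
| Schedule of activities | 1.2: yes, CRF | Table 1.2: no |
| Contact after early discontinuation | 1.2 footnote: yes | Table 1.2 footnote: no |
| Definition or derivation | 10.3.1: yes | 4.2.2.2: no |
| Summary periods | 9.4.3: five | 3.4.3 and 4.2.2.2: none |
| Abbreviation list | 10.7: yes | 6.1: no |

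**2. Which SAP rule would apply to an MAAE.** Protocol 10.3.1 excludes solicited reactions from the MAAE definition. It also defines an unsolicited AE as one that does not meet the conditions of a solicited reaction. An MAAE is therefore an unsolicited AE. The SAP gives separate long windows only to SAEs and AESIs. For an MAAE that is neither, the only onset-timing rule is 4.2.2.2.4:

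- onset in the 21 days after a dose: tabulated with the unsolicited AEs, but not identified as an MAAE;
- missing onset: tabulated in the same way;
- known onset later than that: listed only.

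**3. Days outside the 4.2.2.2.4 window.** The window runs from the dose day to the dose day + 21. The protocol's study-day windows have lengths 42, 202 − 43 + 1 = 160 and 387 − 203 + 1 = 185. Together, 42 + 160 + 185 = 387.

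- *Doses on schedule (D01, D22).* Dose 1 covers D01–D22 and dose 2 covers D22–D43, so D01–D43 is covered.
- *Dose 2 at the end of its +7-day window (D29).* Dose 1 covers D01–D22 and dose 2 covers D29–D50.

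| Protocol window | Uncovered, dose 2 on D22 | Uncovered, dose 2 on D29 |
|---|---|---|
| D01–D42 (42 days) | 0 | 6 (D23–D28) |
| D43–D202 (160 days) | 159 (D44–D202) | 152 (D51–D202) |
| D203–D387 (185 days) | 185 | 185 |
| Total (387 days) | 344 (344/387 = 89%) | 343 (343/387 = 89%) |

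For a dose-2 delay of k = 1 to 7 days, the gap between windows is k − 1 days and the tail is 344 − k days. The total is (k − 1) + (344 − k) = 343, whatever the delay.

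**4. After D387.** Visit 5 may fall up to 14 days late (387 + 14 = D401). With dose 2 on D29, 365 days after the last dose is D394. Onsets after D387 belong only to the protocol's overall-study summary.

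**The case against.** The best reply is that nothing is lost. SAP 3.4 says the core body is used together with the protocol and the SAP tables, listings and figures (TLFs). SAP section 4 says it adds only what the protocol does not detail. The protocol already supplies the MAAE definition, the collection process, the analysis set and the summary periods. SAP rules for intensity, duration and causality of unsolicited AEs carry over. On this view 4.2.2.2.4 limits one set of tables and is no general bar, since SAEs are also unsolicited AEs and are analysed to 387 days. The analyses are descriptive, and dose selection uses data only to 21 days after the last dose.

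Much of this stands as a limit. The endpoint remains pre-specified in the protocol. The TLFs were not supplied and may contain an MAAE table, so the point can be made only about the core body. MAAEs that are also SAEs or AESIs are counted under those headings. Some that lead to discontinuation are counted too, although SAP 4.2.3.6 flags only discontinuation before the end of the intervention phase. The late-period gap does not bear on the dose-selection analysis.

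It does not remove the conflict. SAEs escape 4.2.2.2.4 because the SAP gives them their own window; MAAEs have none. Reading the two documents together sets a protocol instruction to summarise late MAAEs against a SAP instruction to list late unsolicited AEs, with nothing to say which prevails. Nor can the SAE and AESI windows stand in: they are counted from each dose, whereas the protocol's later MAAE windows are study-day intervals. No SAP rule identifies an event as an MAAE in any period.

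**Conclusion.** The point holds; it should be fixed but is not critical. The core body omits one of six secondary safety endpoints. Its only applicable timing rule would leave 344 of 387 nominal study days (343 if dose 2 is given one to seven days late) without a tabulation for MAAEs that are neither serious nor AESIs and have a known onset date. In the remaining days such events are tabulated but not as MAAEs.

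The day count assumes a literal reading of 4.2.2.2.4 and nominal visit days. It measures calendar time and says nothing about how many events are affected, because the documents give no MAAE rate. No primary endpoint is affected, and late events would still be collected and listed.

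The likely cause is a SAP written against protocol version 1.0: the SAP version history shows 27 May 2022, eight days after the date of version 1.0, and MAAE collection is named among the reasons for version 2.0. That is an inference; the documents do not say so.

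**What to change.** Amend the SAP core body before the D43 database lock:

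1. Add MAAEs to Table 2.1 and to 3.4.3, and bring the Table 1.2 schedule and its end-of-study footnote into line with the protocol.
2. State how an MAAE is identified: from the CRF item or, if there is no single item, from a derived flag with its source fields named.
3. State that the D22 exclusion in 4.2.2.2.4 does not apply to MAAE summaries.
4. Tabulate MAAEs on the SafAS by study group and age stratum, in the protocol 9.4.3 windows unchanged, with the overall-study summary taking in events after D387.

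The cost is a text amendment and a few descriptive tables. No new data collection should be needed, since the protocol schedule already marks MAAEs for the CRF, and protocol 9.4 allows the SAP to be amended before database lock. If the TLFs already contain MAAE tables, items 1 to 3 are still needed so that the core body supports them.
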